6.2.4 Concomitant medications

Only those medications that the patient is taking at baseline on a routine basis or medications that cause an AE will be captured in C3D. [Thus onetime medications and PRN medications will not be captured in C3D except those used to treat adverse events.]

6.3 HUMAN DATA SHARING PLANS

6.3.1 Human Data Sharing Plan

6.3.1.1 Human data generated in this research will be shared for future research as follows:

- De-identified data in an NIH-funded or approved public repository
- Identified data in BTRIS

6.3.1.2 Data will be shared through:

- An NIH-funded or approved public repository: clinicaltrials.gov
- BTRIS
- Publication and/or public presentations.

6.3.1.3 Data will be shared at the time of publication or shortly thereafter.

6.3.2 Genomic Data Sharing Plan

Unlinked genomic data will be deposited in public genomic databases such as dbGaP in compliance with the NIH Genomic Data Sharing Policy.

6.4 RESPONSE CRITERIA

For the purposes of this study, patients should be re-evaluated for response every 2 cycles (6 weeks, +/- 3 days).

Response and progression will be evaluated in this study using the new international criteria proposed by the revised Response Evaluation Criteria in Solid Tumors (RECIST) guideline (version 1.1) [*Eur J Ca* 45:228-247, 2009]. Changes in the largest diameter (unidimensional measurement) of the tumor lesions and the shortest diameter in the case of malignant lymph nodes are used in the RECIST criteria.

6.4.1 Definitions

Evaluable for toxicity: All patients will be evaluable for toxicity from the time of their first treatment with CUDC-907.

Evaluable for objective response: Only those patients who have measurable disease present at baseline, have received at least one cycle of therapy, and have had their disease re-evaluated will be considered evaluable for response. These patients will have their response classified according to the definitions stated below. (Note: Patients who exhibit objective disease progression prior to the end of cycle 1 will also be considered evaluable.)

Evaluable Non-Target Disease Response: Patients who have lesions present at baseline that are evaluable but do not meet the definitions of measurable disease, have received at least one cycle of therapy, and have had their disease re-evaluated will be considered evaluable for non-target disease. The response assessment is based on the presence, absence, or unequivocal progression of the lesions.

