CUDC-907 is being studied in 3 early phase clinical trials for the treatment of hematologic malignancies (IND# 115780) and solid tumors (IND# 123500). Under IND# 115780, Curis is conducting 2 trials, a Phase 1 dose escalation and expansion trial in subjects with lymphoma or multiple myeloma and a Phase 2 trial to evaluate CUDC-907 as monotherapy and in combination with rituximab in subjects with relapsed/refractory MYC-altered diffuse large B-cell lymphoma. As of November 2015, a total of 72 subjects have been treated with CUDC-907. In the completed dose-escalation phase, subjects received CUDC-907 daily (QD, doses: 30 or 60 mg), or intermittently on twice weekly or thrice weekly schedules (doses: 60, 90, 120 or 150 mg), or on a 5 days on, 2 days off (5/2) schedule (dose: 60 mg). CUDC-907 dosed at 60 mg on the 5/2 schedule was determined to be the RP2D. Among 58 response-eligible subjects (defined as having received study medication and undergone at least one post-baseline response assessment) with relapsed/refractory lymphoma or multiple myeloma, 3 have achieved confirmed complete response (CR) and 6 have achieved partial response (PR). Another 30 subjects achieved stable disease (SD) (in some cases, of lengthy duration, such as nearly 3 years

in one subject with multiple myeloma) and 19 have experienced progression of disease (PD). CUDC-907 has also been evaluated in patients with advanced solid tumors in a Phase 1 single-agent clinical trial (CUDC-907-102).

Recently, the results of the phase I study on CUDC-907 safety, tolerability, and preliminary activity was reported in 44 enrolled patients (of whom ten were sequentially assigned to CUDC-907 once-daily (maximum tolerated dose {MTD} 60 mg), 12 to twice-weekly (MTD 150 mg), 15 to three-times-weekly (MTD 150 mg), and seven to the 5/2 dosing schedule (MTD 60 mg) [22]. 37 (84%) patients had discontinued study drug as a result of progressive disease or clinical signs of progressive disease at the data cutoff. Four dose-limiting toxicities (DLTs) occurred in three of 40 DLT-evaluable patients (diarrhea and hyperglycemia in one patient on 60 mg once daily, hyperglycemia in one patient on 150 mg twice weekly, and diarrhea in one patient on 150 mg three times weekly) (**Table 2**).

Table 2 CUDC-907 therapy-associated toxicity from phase I trial.[^]

Toxicity	Grade 1–2	Grade 3	Grade 4	Grade 5
Diarrhea	23 (52%)	2 (5%)	0	0
Fatigue	16 (36%)	1 (2%)	0	0
Nausea	11 (25%)	0	0	0

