2.4 STRATIFICATION PROCEDURES

Patients will be stratified in two groups for whom response by the RECIST criteria will be evaluated separately based on the histologic category of thyroid cancer as the aggressiveness of the disease types are significantly different. Group I will include patients with anaplastic thyroid cancer. Group II will include patients with poorly differentiated thyroid cancer and the aggressive variants of differentiated thyroid cancer. Up to 20 evaluable patients will be enrolled to each cohort using a Simon Minimax two-stage phase II trial design as described in section 8.

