8 STATISTICAL CONSIDERATIONS

The primary objective of this trial is to determine the objective response rate of patients with locally advanced and or metastatic poorly differentiated and anaplastic thyroid cancer, and aggressive variants of differentiated thyroid cancer.

Patients will be enrolled into separate cohorts in order to estimate the response rates in each cohort: 1: Anaplastic thyroid cancer; 2: Poorly differentiated and aggressive variants of

differentiated thyroid cancer. Since there is no reliable information on expected clinical response rates in either cohort, each will be evaluated individually, with the primary objective in each cohort being to determine if using CUDC-907 would rule out a 5% response rate and target a rate of 25%. As such, in each cohort, the trial will be conducted using a Simon Minimax two-stage phase II trial design in order to rule out an unacceptably low partial (PR) + complete response (CR) rate of 5% ($p_0=0.05$) in favor of an improved response rate of 25% ($p_1=0.25$) [18]. With $\alpha=0.10$ (probability of accepting a poor treatment=0.10) and $\beta = 0.10$ (probability of rejecting a good treatment=0.10), this first stage will enroll 13 evaluable patients in a given cohort, and if 0 of the 13 have a clinical response, then no further patients will be accrued to that cohort. If 1 or more of the first 13 patients have a response in that cohort, then accrual would continue until a total of 20 evaluable patients have been treated in that cohort. As it may take up to several months to determine if a patient has experienced a response, a temporary pause in the accrual may be necessary to ensure that enrollment to the second stage is warranted. If there are 1 to 2 patients with a response out of 20 patients in a cohort, this would be an uninterestingly low response rate. If there were 3 or more of 20 (15%) who experienced a response, this would be sufficiently interesting to warrant further study in later trials with that cohort. Under the null hypothesis (5% response rate), the probability of early termination in either cohort is 51.3%.

In order to ensure that it remains safe to accrue patients, toxicity will be monitored in all patients. If at any time after 6 or more patients have been accrued in both cohorts combined, the cumulative fraction of patients with DLTs is 1/3 or greater, then no further patients will be enrolled on the trial.

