Any secondary evaluations performed will be done in an exploratory fashion, with results presented without any formal adjustment for multiple comparisons.

It is anticipated that approximately 6 to 8 patients per year may enroll onto the trial. Thus, accrual of up to 40 total evaluable patients may be completed in approximately 5 to 7 years. In order to allow for a small number of in evaluable patients, the accrual ceiling will be set to 50 patients.

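### The primary response rate leaves out treated patients who are not evaluable, and no all-treated rate is planned beside it; if any such patients occur, the rate very probably overstates response among patients started on CUDC-907

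*Combined protocol and SAP*

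**What the plan says.** Section 6.4.1 (Definitions) restricts response evaluation to "Only those patients who have measurable disease present at baseline, have received at least one cycle of therapy, and have had their disease re-evaluated". A note adds patients whose disease objectively progresses before cycle 1 is complete. The same section makes every patient evaluable for toxicity from the first dose; it defines no matching population for response.

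Section 2.4 sets cohort size in the same unit: "Up to 20 evaluable patients will be enrolled to each cohort using a Simon Minimax two-stage phase II trial design". Section 8 does so for the interim look: "this first stage will enroll 13 evaluable patients in a given cohort, and if 0 of the 13 have a clinical response", accrual to that cohort stops. Otherwise it continues to 20 evaluable patients, and 3 or more responses warrant further study.

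On losses, Section 8 says that, to "allow for a small number of in evaluable patients, the accrual ceiling will be set to 50" patients, against a target of 40 evaluable. Its only sentence on secondary evaluations says they are exploratory and unadjusted for multiplicity. No section plans a response rate over all treated patients or says how a treated patient without a re-evaluation is to be classified.

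**The concern.** Two groups of treated patients fall outside the definition:

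- patients who received less than one cycle and had no objective progression in that time, even if they are scanned later;
- patients who completed a cycle but died, deteriorated or withdrew before any re-evaluation.

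The first scheduled restaging comes after two cycles, at about 6 weeks (Sections 3.7 and 6.4), so there is time for such losses. They are not random with respect to outcome. Without a re-evaluation no response can be recorded, so the patients removed from the denominator are almost all non-responders, and the spare places allow others to be enrolled in their stead.

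What is at stake is how the result is read. Section 10.5 says that a tumor response would lead to consideration of a large multicenter trial. That decision needs the response rate among patients started on CUDC-907. The plan would supply only the rate among those who reached a qualifying re-evaluation.

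**Working it through.** **Inputs.** From Section 8: p0 = 0.05, p1 = 0.25, stage 1 of 13 (stop at 0 responses), total 20 (success at 3 or more), target 40 evaluable, ceiling 50. From Section 1.2: earlier CUDC-907 response counts. The share d of treated patients excluded from the evaluable set is not given, so it is an assumption, shown at 10% and 20%.

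**1. The plan's own figures.**
- Early termination at 5%: 0.95^13 = 0.513, matching the stated 51.3%.
- Probability of success at rate p: the sum over x = 1 to 13 of P(X1 = x) × P(X2 ≥ 3 - x), with X1 ~ Bin(13, p) and X2 ~ Bin(7, p).
- At p = 0.05 this is 0.074; at p = 0.25 it is 0.903. Both meet the limits of 0.10 and 0.90.
- A search over two-stage designs confirms 0/13 then 2/20 as the minimax choice.

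**2. Size of the overstatement.** With T treated patients, T(1-d) evaluable and R responses, the reported rate is R/[T(1-d)]. If no excluded patient responded, the all-treated rate is R/T and the ratio is 1/(1-d).
- d = 10%: 1/0.90 = 1.11.
- d = 20%: 1/0.80 = 1.25.

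This is a maximum. A patient scanned after less than one cycle might have responded, and that would lower the ratio.

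**3. At the success boundary.**
- 3/20 = 15.0% of evaluable patients (exact 95% CI 3.2% to 37.9%).
- Two dosed exclusions in the cohort: 3/22 = 13.6%.
- Five dosed exclusions in the cohort: 3/25 = 12.0% (exact 95% CI 2.5% to 31.2%).

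**4. What the ceiling allows.** With both cohorts filled, 50 - 40 = 10 spare places, or 10/50 = 20% overall. Section 2.3 registers a candidate within 24 hours of consent and before drug is released, so some of these places may go to patients never dosed. For treated patients, 20% is therefore an extreme and not an estimate. The ceiling applies to the whole trial. One cohort could reach 10/30 = 33% only if all ten places fell in it and all ten patients were dosed.

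**5. Earlier data, as illustration only (Section 1.2).**
- "As of November 2015, a total of 72 subjects have been treated with CUDC-907"; 58 were response-eligible, with 3 + 6 = 9 responses. 9/58 = 15.5% against 9/72 = 12.5%, ratio 1.24.
- Published phase I study: 5/37 = 13.5% of response-evaluable against 5/44 = 11.4% of enrolled patients, ratio 1.19.

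These are lymphoma and myeloma populations. The two counts may overlap, and some patients may have been awaiting a scan. The rule behind the 58 also differs from Section 6.4.1: any study drug plus one post-baseline assessment, with no one-cycle minimum. The figures show the direction of the effect but do not size it for this trial.

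**The case against.** The strongest reply is that an evaluable-patient analysis is prespecified, applied consistently in Sections 2.4, 6.4.1 and 8, and narrower in its losses than it first appears. Patients with objective progression in cycle 1 stay in, including those whose superficial lesions are measured with calipers (Section 6.4.3). Section 3.9 seeks a safety visit with CT or MRI about 30 days after the last dose, so a patient who stops after a full cycle and attends becomes evaluable. Early deaths are not hidden either: overall survival is a secondary objective, and all treated patients count for toxicity.

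All of this is correct, and it limits the number lost. It does not remove the gap. The safety-visit scan depends on attendance and cannot restore a patient given less than one cycle without early objective progression. Survival and toxicity reporting do not yield a response rate.

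A reader might also infer that the type I error exceeds 0.10. That would follow if 5% were an all-treated rate and excluded patients never responded: the evaluable rate would then be 0.05/(1-d), and the error would pass 0.10 at d = 12.3% and reach 0.123 at 20%. The documents do not support this reading. Section 8 attaches both stage sizes to evaluable patients and derives the rates from no outside benchmark: "Since there is no reliable information on expected clinical response rates in either cohort". Even on that reading, if excluded patients responded at half the overall rate, d = 20% gives an evaluable rate of (0.05 - 0.20 × 0.025)/0.80 = 0.056 and an error of 0.097.

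**Conclusion.** The point stands as a reporting gap. Following the plan exactly, treated patients without a qualifying re-evaluation leave the denominator, and no companion rate shows the effect. If any such patients occur, the reported rate will very probably overstate response among patients started on CUDC-907, by at most 1/(1-d). The 1.11-fold and 1.25-fold figures rest on assumed exclusion shares of 10% and 20% and on no response among excluded patients.

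Three stronger conclusions are not supported:

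- That the rate is certain to be overstated. If every dosed patient is evaluable, the two rates coincide, and the plan expects few losses.
- That the earlier CUDC-907 figures measure the effect here. They come from other diseases and, for the 58, a different evaluability rule.
- That the anaplastic cohort is shown to lose more. A median survival of 4.9 months (Section 1.2) makes this plausible, but the documents do not quantify it, and entry is limited to ECOG 0 to 2 without CNS metastases.

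The Simon design is sound on its own terms, and no error-rate breach is shown.

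**What to change.** In Sections 6.4.1 and 8:

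1. For each cohort, report the response rate with exact confidence interval among all patients with measurable disease at baseline who received at least one dose. Count those with no post-baseline re-evaluation as non-responders. Classify anyone who was re-evaluated by that result, even if less than one cycle was given.
2. Report the number excluded from the evaluable set by cohort, with reasons, separating patients never dosed from those dosed.
3. State that 5%, 25%, 0/13 and 3/20 refer to evaluable patients.

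This needs wording only: no extra patients, visits or scans. The downside is a slightly lower figure beside the primary one.

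Making the all-treated set primary, without replacing dosed patients, is optional and not part of the required fix. It changes the quantity being estimated. If 25% were declared an all-treated target, power at 13/20 would stay 0.903. If 25% is an evaluable-patient target, the all-treated rate is 0.25(1-d), and power falls to 0.854 at 10% excluded (rate 0.225) and 0.786 at 20% (rate 0.20). Power would then have to be restated.

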6.4.2 Disease Parameters

Measurable disease: Measurable lesions are defined as those that can be accurately measured in at least one dimension (longest diameter to be recorded) as ≥ 20 mm by chest x-ray, as ≥ 10 mm with CT scan, or ≥ 10 mm with calipers by clinical exam. All tumor measurements must be recorded in millimeters (or decimal fractions of centimeters).

Malignant lymph nodes. To be considered pathologically enlarged and measurable, a lymph node must be ≥ 15 mm in short axis when assessed by CT scan (CT scan slice thickness recommended to be no greater than 5 mm). At baseline and in follow-up, only the short axis will be measured and followed.

Non-measurable disease. All other lesions (or sites of disease), including small lesions (longest diameter < 10 mm or pathological lymph nodes with ≥ 10 to < 15 mm short axis), are considered non-measurable disease. Bone lesions, leptomeningeal disease, ascites, pleural/pericardial effusions, lymphangitis cutis/pulmonitis, inflammatory breast disease, and abdominal masses (not followed by CT or MRI), are considered as non-measurable.

Note: Cystic lesions that meet the criteria for radiographically defined simple cysts should not be considered as malignant lesions (neither measurable nor non-measurable) since they are, by definition, simple cysts.

‘Cystic lesions’ thought to represent cystic metastases can be considered as measurable lesions, if they meet the definition of measurability described above. However, if non-cystic lesions are present in the same patient, these are preferred for selection as target lesions.

Target lesions. All measurable lesions up to a maximum of 2 lesions per organ and 5 lesions in total, representative of all involved organs, should be identified as **target lesions** and recorded

and measured at baseline. Target lesions should be selected on the basis of their size (lesions with the longest diameter), be representative of all involved organs, but in addition should be those that lend themselves to reproducible repeated measurements. It may be the case that, on occasion, the largest lesion does not lend itself to reproducible measurement in which circumstance the next largest lesion which can be measured reproducibly should be selected. A sum of the diameters (longest for non-nodal lesions, short axis for nodal lesions) for all target lesions will be calculated and reported as the baseline sum diameters. If lymph nodes are to be included in the sum, then only the short axis is added into the sum. The baseline sum diameters will be used as reference to further characterize any objective tumor regression in the measurable dimension of the disease.

Non-target lesions. All other lesions (or sites of disease) including any measurable lesions over and above the 5 target lesions should be identified as **non-target lesions** and should also be recorded at baseline. Measurements of these lesions are not required, but the presence, absence, or in rare cases unequivocal progression of each should be noted throughout follow-up.

6.4.3 Methods for Evaluation of Measurable Disease

All measurements should be taken and recorded in metric notation using a ruler or calipers. All baseline evaluations should be performed as closely as possible to the beginning of treatment and never more than 4 weeks before the beginning of the treatment.

The same method of assessment and the same technique should be used to characterize each identified and reported lesion at baseline and during follow-up. Imaging-based evaluation is preferred to evaluation by clinical examination unless the lesion(s) being followed cannot be imaged but are assessable by clinical exam.

Clinical lesions: Clinical lesions will only be considered measurable when they are superficial (e.g., skin nodules and palpable lymph nodes) and ≥ 10 mm diameter as assessed using calipers (e.g., skin nodules). In the case of skin lesions, documentation by color photography, including a ruler to estimate the size of the lesion, is recommended.

Chest x-ray: Lesions on chest x-ray are acceptable as measurable lesions when they are clearly defined and surrounded by aerated lung. However, CT is preferable.

Conventional CT and MRI: This guideline has defined measurability of lesions on CT scan based on the assumption that CT slice thickness is 5 mm or less. If CT scans have slice thickness greater than 5 mm, the minimum size for a measurable lesion should be twice the slice thickness. MRI is also acceptable in certain situations (e.g. for body scans).

Use of MRI remains a complex issue. MRI has excellent contrast, spatial, and temporal resolution; however, there are many image acquisition variables involved in MRI, which greatly impact image quality, lesion conspicuity, and measurement. Furthermore, the availability of MRI is variable globally. As with CT, if an MRI is performed, the technical specifications of the scanning sequences used should be optimized for the evaluation of the type and site of disease. Furthermore, as with CT, the modality used at follow-up should be the same as was used at baseline and the lesions should be measured/assessed on the same pulse sequence. It is beyond the scope of the RECIST guidelines to prescribe specific MRI pulse sequence parameters for all scanners, body parts, and diseases. Ideally, the same type of scanner should be used and the

image acquisition protocol should be followed as closely as possible to prior scans. Body scans should be performed with breath-hold scanning techniques, if possible.

Ultrasound: Ultrasound is not useful in assessment of lesion size and should not be used as a method of measurement. Ultrasound examinations cannot be reproduced in their entirety for independent review at a later date and, because they are operator dependent, it cannot be guaranteed that the same technique and measurements will be taken from one assessment to the next. If new lesions are identified by ultrasound in the course of the study, confirmation by CT or MRI is advised. If there is concern about radiation exposure at CT, MRI may be used instead of CT in selected instances.

FDG-PET: While FDG-PET response assessments need additional study, it is sometimes reasonable to incorporate the use of FDG-PET scanning to complement CT scanning in assessment of progression (particularly possible 'new' disease). New lesions on the basis of FDG-PET imaging can be identified according to the following algorithm:

- a. Negative FDG-PET at baseline, with a positive FDG-PET at follow-up is a sign of PD based on a new lesion.
- b. No FDG-PET at baseline and a positive FDG-PET at follow-up: If the positive FDG-PET at follow-up corresponds to a new site of disease confirmed by CT, this is PD. If the positive FDG-PET at follow-up is not confirmed as a new site of disease on CT, additional follow-up CT scans are needed to determine if there is truly progression occurring at that site (if so, the date of PD will be the date of the initial abnormal FDG-PET scan). If the positive FDG-PET at follow-up corresponds to a pre-existing site of disease on CT that is not progressing on the basis of the anatomic images, this is not PD.
- c. FDG-PET may be used to upgrade a response to a CR in a manner similar to a biopsy in cases where a residual radiographic abnormality is thought to represent fibrosis or scarring. The use of FDG-PET in this circumstance should be prospectively described in the protocol and supported by disease-specific medical literature for the indication. However, it must be acknowledged that both approaches may lead to false positive CR due to limitations of FDG-PET and biopsy resolution/sensitivity.

Note: A 'positive' FDG-PET scan lesion means one which is FDG avid with an uptake greater than twice that of the surrounding tissue on the attenuation corrected image.

